2.5.4 Minimization of Bias

There will be no specific sex, ethnic or racial background for enrollment. Placebo arm is introduced to increase the ability to differentiate between the pharmacologic effects of lidocaine and other possible effects. The study is designed as cross-over in order to minimize inter-subject variability. The investigators and the subjects will be blinded to treatment allocation sequence. Plasma lidocaine concentration is not affected by subjects' or investigators' knowledge of study aims and hypothesis.

2.5.5 Observations and Measurements

2.5.5.1 Primary Outcome Measures

Primary outcome:

Reduction in spontaneous pain intensity on 0-10 NRS in the feet at 50 minutes after beginning the intravenous lidocaine infusion. This endpoint is calculated as the average of pain intensities measured at 40, 50 and 60 min after beginning of the infusion.

2.5.5.2 Secondary Outcome Measures

Secondary outcomes:

- 1). Change in the intensity (0-10 scale) of evoked mechanical and thermal sensation: cold, warm, brush and pinprick.
- 2). Change in the NPSI descriptors of pain (burning, squeezing, pins and needles, tingling, stabbing, electrical shocks) on 0-10 scale at 60 min post-infusion.
- 3). Multiple regression analysis to investigate how the combination of various sensory phenotypes assessed in this study (i.e. MPT, HPT, MDT, WDT, CDT, CPT, and CPM) and lidocaine pharmacokinetics (area under the concentration-time curve, (AUC) and maximal plasma concentration (Cmax)) correlate with treatment response to lidocaine.

2.5.6 QST protocol

Quantitative sensory testing will be performed on the dorsal mid-foot. If asymmetry in pain intensity exists between extremities, QST will be performed in the more painful foot; otherwise the foot will be chosen randomly. The ipsilateral shoulder will serve as control area.

A description of the QST procedures follows:

Thermal detection and thermal pain thresholds

Equipment: The Thermal Sensory Analyzer (TSA-II platform - Medoc, Ramat Yishai, Israel) will be used to determine thermal detection and pain thresholds. This equipment is used globally for functional assessment of pain and temperature-conducting nerve fibers (C and A-delta fibers).

Method and Background: Using the thermal sensory analyzer, cold and warm detection thresholds (CDT and WDT, respectively), as well as cold and heat pain thresholds (CPT and HPT, respectively) will be determined [23, 24]. The thermode with contact area of 9.0 cm² is applied to the tested site, and all thresholds are determined by continuous ramping of temperature from 32°C baseline temperature by 1°C/s until the subject presses the ‘stop’ button. Cut-off temperatures are 0°C and 50°C, to minimize thermal damage to the skin. The baseline temperature to which the thermode returns before each test is 32°C. The average threshold is calculated from three measurements in each area.

Determination of mechanical detection threshold (MDT)

Equipment: A set of standardised von Frey filaments (0.25, 0.5, 1, 2, 4, 8, 16, 32, 64, 128 and 256mN). The contact area of the hairs with the skin is of uniform size (<1 mm²) and texture.

Methods and Background: Standardised von Frey filaments will be used in a modified “method of limits” manner using 3 series of increasing and decreasing stimulus intensities to determine the geometric average as the tactile detection threshold of the affected and unaffected skin areas [25].

Von Frey filaments of different stimulus intensities are used to determine the tactile detection thresholds. A filament eliciting 16mN force* is applied first, followed by filaments of consecutively lower intensity until the patient cannot detect the stimulus being applied. This respective force represents the first threshold value. The order in which the stimuli are applied is then reversed and stimuli of consecutively greater intensity are applied until sensation is detected (this intensity becomes the second value). Again filaments with decreasing intensity are applied until in total 3 upper and lower values of detection are fulfilled from which the mechanical detection threshold can be determined.

* In case the first von Frey filament with an intensity of 16mN is not detected, the next highest intensity filament which can be detected must be used as a starting intensity. However, the relevant force of this stimulus is not documented. Filaments with consecutively lower intensity are applied until the patient

cannot detect the stimulus being applied. The procedure is followed as above; until in total 3 upper and lower values of detection are fulfilled from which the mechanical detection threshold can be determined.

Determination of mechanical pain thresholds (MPT)

Equipment: A set of standardized weighted metal probes (Nervetest, MRC systems) exerting pressure of 8, 16, 32, 64, 128, 256 and 512 mN.

Methods and Background:

The standardized metal probes will be used in a modified method of levels manner, 3 series of increasing stimulus intensities to detect the mechanical pain threshold. Beginning with an applied force of 8mN, stimuli increase in intensity until the sensation induced by increased pressure can be described as 'painful'. The corresponding force is used to represent the first MPT value. The procedure is then repeated a total of 3 times and until a total of 3 values are obtained, from which the mean MPT is determined.

Determination of wind-up ratio (WUR)

Equipment: A standardized weighted metal probes (Nervetest, MRC systems) exerting pressure of 256mN.

[figure not shown]
Methods and Background: In this test a pinprick (256mN) is first applied singularly. After that a series of 10 identical pinprick stimuli are applied with a frequency of 1 s^{-1} within an area of 1 cm^2 . Immediately following the single stimulus and series of stimuli, an evaluation of the sensation must be provided according to NRS (0-10, '0': 'no pain', '10': 'worst pain imaginable'). A ratio is calculated using these values. This procedure will be repeated twice. A geometric average of the 'wind-up' is calculated from the two ratios [26, 27].

Determination of conditioned pain modulation (CPM) efficiency

Equipment: The Q-Sense Thermal Analyzer (Medoc, Ramat Yishai, Israel) will be used for CPM paradigm testing.

Methods and Background

The Q-Sense works on the same principle as TSA-II, which is used for determining the thermal thresholds. However, Q-Sense is equipped with two 3x3cm Peltier thermodes – one used as conditioning stimulus, and the other used as test stimulus. The intensity of the conditioning stimulus will be determined individually by temperature that elicits pain intensity of 30 on 0-100 NRS. The intensity of test stimulus will also be determined individually, at the temperature that elicits pain intensity of 60 on 0-100 NRS. The conditioning stimulus will be applied at left shoulder, while the test stimulus will be applied at the right shoulder. The length of the conditioning stimulus is 60 seconds, during the last 30 seconds of which the pain stimulus is applied. The stimuli are applied according to the diagram in Fig.3 below – and the difference between the intensity of pain stimulus without conditioning and between the intensity of pain stimulus with concomitant conditioning is the CPM magnitude. $\text{CPM} > 0$ implies efficient descending pain modulation.

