2.5 Design and Procedures

2.5.1 Study Design

This is a prospective, randomized, double-blind, placebo-controlled, cross-over study in 35 patients with painful DPN. If our hypothesis is confirmed, then patients with higher MPT or HPT at baseline will have larger analgesic effect from lidocaine infusion.

Randomization and Blinding

Eligible patients will attend a screening visit and two intervention visits, during which intravenous lidocaine or placebo infusion will be administered in a cross-over design. At enrollment, each patient will be assigned a study number, which will match a previously prepared computer-generated list of randomization numbers to determine the sequence of interventions: lidocaine and then placebo, or *vice versa*. An unblinded investigator will be assigned to match the study number with randomized treatment sequence, and this person will prepare the study medications, which will look identical. This investigator will not be involved at any stage at patient assessment or data analysis. The participants and all other study personnel will be blinded to the treatment allocation.

Sample size

In order to identify significant differences in slopes of predictor of response magnitude vs pain reduction curve in lidocaine group and placebo group, 34 patients will be required for this cross-over trial. The calculation is based on the ability to detect difference of 14 (SD 18.21) units between correlation coefficients of the two curves, based on our pilot data [14] (the calculation was performed for 85% power, and $\alpha = 0.025$, after Bonferroni correction for two comparisons; MPT and HPT). The enrollment will continue until 35 participants have completed both phases of treatment.

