2.5.7 Statistical Methods

The comparison between the analgesic effectiveness associated with each putative predictor of response (MPT and HPT) to lidocaine and to placebo will be performed by the following method: We will perform t-test in a multiple linear regression model to test the difference between slopes of predictor magnitude vs. response magnitude, namely: 1) Compare the slopes of MPT magnitude vs. lidocaine response magnitude (% reduction in pain intensity) curve, and MPT magnitude vs. placebo response magnitude (% reduction in pain intensity) curve. The same procedure will be performed for HPT predictor.

The time point for primary effectiveness (pain reduction) outcome is 50 min after beginning of the infusion, based on our preliminary data. This will be calculated from the average of pain intensities at 40, 50 and 60 min from the beginning of the infusion.

The time point for secondary outcome of change in NPSI pain descriptors is 45 min after beginning of the infusion.

In exploratory phase, multiple regression analysis will be performed to investigate how the combination of various sensory phenotypes assessed in this study (i.e. MPT, HPT, WDT, MDT, CDT, CPT, and CPM) and lidocaine pharmacokinetics (area under the concentration-time curve, (AUC) and maximal plasma concentration (Cmax)) correlate with treatment response to lidocaine.

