2.5.8 Sample Size

In order to identify significant differences in slopes of predictor of response magnitude vs pain reduction curve in lidocaine group and placebo group, 34 patients will be required for this cross-over trial. The calculation is based on the ability to detect difference of 14 (SD 18.21) units between correlation coefficients of the two curves, based on our pilot data [14] (the calculation was performed for 85% power, and $\alpha = 0.025$, after Bonferroni correction for two comparisons; MPT and HPT). The enrollment will continue until 35 participants have completed both phases of treatment.

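### Does leaving the scale, type of mean and 512 mN ceiling value for mechanical pain threshold (MPT) unstated undermine the primary MPT test?

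*Combined protocol and SAP*

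**What the plan says.** The MPT paragraph of 2.5.6 QST protocol describes weighted probes "exerting pressure of 8, 16, 32, 64, 128, 256 and 512 mN". Force is raised until the patient calls it painful, that force is recorded, and three series are run "until a total of 3 values are obtained, from which the mean MPT is determined". The same section asks for a geometric average for the mechanical detection threshold and the wind-up ratio, but says only mean for MPT. For heat pain threshold (HPT) it gives limits: "Cut-off temperatures are 0°C and 50°C, to minimize thermal damage to the skin".

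2.5.7 Statistical Methods sets the primary test: "Compare the slopes of MPT magnitude vs. lidocaine response magnitude (% reduction in pain intensity) curve", against the matching placebo curve, and the same for HPT. It mentions no transformation.

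2.5.8 Sample Size, repeated in 2.5.1, asks for 34 patients at 85% power and alpha 0.025, "after Bonferroni correction for two comparisons; MPT and HPT". The planning effect is a "difference of 14 (SD 18.21) units between correlation coefficients of the two curves", taken from the pilot. The same paragraph speaks of slopes.

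**The concern.** MPT carries one of the two primary tests, and its probes double at each step, so a log scale is a natural alternative to raw mN. The two can differ a good deal: three series at 32, 128 and 512 mN average 224 mN arithmetically and 128 mN geometrically. A patient who finds 512 mN painless has no recorded value in the text.

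The planning figure seems to make this worse. Read as a slope on raw mN, 14 points of pain reduction per mN is 14 × 504 = 7,056 points from the lowest probe to the highest. Per doubling it is 14 × 6 = 84 points, which is possible. That suggests the pilot worked on a log scale while the plan is written in mN. If so, the stated 85% power would belong to a different model, and the scale and ceiling code could be chosen after the data are seen.

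**Working it through.** **1. The plan's own figure.** Inputs from 2.5.8: difference 14, SD 18.21, power 85%, alpha 0.025 (two-sided assumed, since sidedness is not stated).

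- Paired: n = (z₀.₉₈₇₅ + z₀.₈₅)² × (SD/difference)² = (2.241 + 1.036)² × (18.21/14)² = 10.74 × 1.692 = 18.2, so 19 (21 with the t distribution).
- Two independent groups: 2 × 18.18 = 36.4, so 37 per group (38 with t).
- If 18.21 is a per-period SD, the paired t needs 39, 36, 32 or 21 patients at within-patient correlation 0, 0.1, 0.2 or 0.5. No correlation is stated.

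The stated 34 is not reproduced by a version that fits the stated design and inputs. None of these formulas contains the spread of the predictor, so an MPT scale cannot be recovered from them.

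**2. What 14 could be.**

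- A difference between two correlations cannot exceed 2, so the literal wording fails on any MPT scale.
- As a slope for HPT, 14 per °C is 14 × 5 = 70 points over 45–50°C. That is possible in the stated unit.
- As a difference in mean percent reduction, it carries no predictor scale.
- As a slope for MPT, see step 3.

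**3. Is 14 per mN impossible?** Let D be a patient's lidocaine-minus-placebo percent reduction. The slope is r × SD(D)/SD(MPT), so its size is at most max|D|/SD(MPT). For a slope of 14, SD(MPT) can be at most:

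| Range of each response | max\|D\| | Largest SD(MPT) for slope 14 | Largest slope at SD 170 mN |
|---|---|---|---|
| 0 to 100% | 100 | 100/14 = 7.1 mN | 0.6 |
| −100 to 100% | 200 | 14.3 mN | 1.2 |
| −150 to 100% (pain 4 rising to 10) | 250 | 17.9 mN | 1.5 |
| −900 to 100% (pain 1 rising to 10) | 1,000 | 71 mN | 5.9 |

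Equal use of the seven probes gives an SD of about 170 mN. So 14 per mN is not credible for a spread-out cohort, but it is not arithmetically impossible. Put all thresholds on the 8 and 16 mN probes, with lidocaine response rising from 0 to 56% (56/8 = 7 per mN) and placebo response falling from 56 to 0% (−7 per mN). The difference is exactly 14.

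Nor does dividing the full span of D by the probe range (500/504 = 0.99) bound a regression slope. Take one patient per probe, with D = +250 above the mean threshold of 145 mN and −250 below it. The least-squares slope is then 2 × 250 × 477.7/202,039 = 1.18.

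**4. What the scale and ceiling choices do to the test.** The simulation assumes n = 35, alpha 0.025, and a correlation of 0.52 (85% power without a ceiling). It uses five MPT distributions with 3–24% of patients off-scale in all three series, and keeps every patient. The documents give neither the distributions nor the off-scale share.

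| True relation | Raw mN, 512 recorded | Log2, 512 recorded | Raw minus log2 |
|---|---|---|---|
| Linear in log2 | 0.75–0.78 | 0.74–0.81 | −3.3 to +1.0 points |
| Linear in mN | 0.60–0.68 | 0.49–0.54 | +11.1 to +17.6 points |

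The differences are taken within each distribution, for example 0.767 − 0.800 = −0.033 and 0.676 − 0.500 = +0.176.

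Type I error was 0.024–0.026 for any one fixed choice, 0.032–0.036 for the better of two scales, and 0.043–0.046 for the best of two scales and two ceiling codes (512 and 1024 mN).

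A second simulation assumed 7 points per doubling, residual SD 25, and about 18% of patients with at least one series above 512 mN. It gave power of 58% (log), 55% (raw, 512 recorded) and 52% (raw, 1024 recorded).

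**The case for a change.** The best case for a change is that two competent analysts could run the MPT test differently. In the first simulation the raw and log2 conclusions differed in 8–10% of trials when response was linear in log2 and in 13–20% when it was linear in mN. The 512 and 1024 mN codes differed in 11–22% on raw mN. One sentence before unblinding would settle this at no cost, and the plan is more explicit for its lesser measures.

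Part of this stands. The wording is thinner for MPT than for detection threshold and wind-up, and the label on the planning figure is wrong.

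The rest does not amount to a fault in the analysis. Because geometric averaging is named where it is wanted, a plain mean in the only unit given is readable as arithmetic mN. Disagreement between two valid analyses is not error in either one. The inflated type I error needs someone to run several versions and keep the best, and nothing in the plan invites that. Nothing says off-scale patients are dropped, so a large power loss from discarding them is not a consequence of the text.

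Nor is there a clearly better rule to write in. Neither scale wins in both cases. Recording 512 mN at the ceiling gave less power than 1024 mN in 17 of 20 combinations of distribution, scale and true relation, yet 1024 mN is not a probe in the set. Under the mN-linear cases, which cap true thresholds at 1024 mN, that code gained 8 to 19 points. Those cases favour it by construction.

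**Conclusion.** No change to the MPT analysis follows. This is detail that analysts fill sensibly: average the three forces in mN, record the top probe or the 50°C cut-off when the limit is reached, and keep the patient. On that reading the test holds its 0.025 level. Against log2 it costs at most about 3 points of power in the log2-linear cases and gains 11 to 18 in the mN-linear ones. These figures rest on assumed distributions and an assumed correlation, so they illustrate and do not forecast.

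The planning figure is a separate loose end. As labelled, 14 cannot be right, and 34 is not reproduced (19–21 paired, 37–38 per group for independent groups). That is a question about what quantity 2.5.8 powers. A figure of unknown type cannot show that the pilot used a log scale, and fixing the MPT scale would not repair it. Figure 2 is not in the copy reviewed. The pilot report and the sensory-testing reference cited in 2.5.3 were not available either, and any of the three may already settle the scale or the ceiling value.

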2.5.7 Statistical Methods

The comparison between the analgesic effectiveness associated with each putative predictor of response (MPT and HPT) to lidocaine and to placebo will be performed by the following method: We will perform t-test in a multiple linear regression model to test the difference between slopes of predictor magnitude vs. response magnitude, namely: 1) Compare the slopes of MPT magnitude vs. lidocaine response magnitude (% reduction in pain intensity) curve, and MPT magnitude vs. placebo response magnitude (% reduction in pain intensity) curve. The same procedure will be performed for HPT predictor.

The time point for primary effectiveness (pain reduction) outcome is 50 min after beginning of the infusion, based on our preliminary data. This will be calculated from the average of pain intensities at 40, 50 and 60 min from the beginning of the infusion.

The time point for secondary outcome of change in NPSI pain descriptors is 45 min after beginning of the infusion.

In exploratory phase, multiple regression analysis will be performed to investigate how the combination of various sensory phenotypes assessed in this study (i.e. MPT, HPT, WDT, MDT, CDT, CPT, and CPM) and lidocaine pharmacokinetics (area under the concentration-time curve, (AUC) and maximal plasma concentration (Cmax)) correlate with treatment response to lidocaine.

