	
Testing for intervention response (repetitive testing):
 
 1. Spontaneous pain intensity on 0-10 NRS and 0-100 computerized visual analog scale (CoVAS); 2. Response to warm, cold, pinprick and brush stimuli on 0-10 scale (0 -not felt, 5 – normal, 10 - most intensely felt); 3. Pain descriptors on NPSI questionnaire (burning, squeezing, pins and needles, tingling, stabbing, electrical shocks) on 0-10 scale; 4. Measurement of nociception level (NoL) index with finger probe (PMD 100 device); 5. Lidocaine plasma concentrations.

Statistical Methodology
	
The comparison between the analgesic effectiveness associated with each putative predictor of response (MPT and HPT) to lidocaine and to placebo will be performed by the following method: We will perform t-test in a multiple linear regression model to test the difference between slopes of predictor magnitude vs. response magnitude, namely: 1) Compare the slopes of MPT magnitude vs. lidocaine response magnitude (% reduction in pain intensity) curve, and MPT magnitude vs. placebo response magnitude (% reduction in pain intensity) curve. The same procedure will be performed for HPT predictor. The time point for primary effectiveness (pain reduction) outcome is the average of pain intensity measured at 40, 50 and 60 min after beginning of the infusion.

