2.3 Objective

The objective of the proposed study is to test whether quantitative sensory measures predict the response to treatment with systemic sodium channel blocker lidocaine in patients with painful DPN.

The specific aims of this study are:

1. To investigate whether the baseline mechanical pain threshold (MPT) predicts the individual response to intravenous lidocaine treatment in DPN.
2. To investigate whether the baseline heat pain threshold (HPT) predicts the individual response to intravenous lidocaine treatment in DPN.

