2.5.3 Study Period

Subjects will be studied in the Washington University Pain Management Center. Eligible subjects will attend two treatment visits, during which intravenous lidocaine or placebo infusion will be administered in randomized order in double-blinded fashion. Subjects are instructed to refrain from eating 4 hours prior to the lidocaine infusion, but can drink clear liquids up to 2 hours prior to the procedure. The infusion start will be planned approximately at 10am; therefore subjects will be allowed to have a light snack before 6am if required for taking their DM medications (e.g. metformin). At each of these visits the subjects will undergo a quantitative sensory testing procedure to determine the MPT and HPT parameters [15]. MPT will be measured using a standardized weighted metal probes (Nervetest, MRC systems) using a modified method of levels, and HPT will be measured with Thermal Sensory Analyzer (TSA-II, Medoc, Israel) using the method of limits. In addition, other quantitative sensory measures will be obtained to better characterize the underlying nerve damage and possible pain mechanism. Namely, we will assess mechanical detection threshold (MDT) with von Frey filaments, cold and warm detection thresholds (CDT and WDT), as well as cold pain threshold (CPT) with TSA-II device, per previously published standard protocol [13, 15]. We will also apply conditioned pain modulation (CPM) protocol to assess the efficiency of descending inhibitory pain controls, as this was suggested to predict response to treatment in DPN [10], and lidocaine was shown to affect the descending inhibitory controls [16]. CPM protocol will tests whether concomitant application (conditioning) of a mildly painful stimulus on an upper extremity

(heat that elicits individually calibrated pain intensity of 30 on 0-100 NRS) reduces the painful experience from a painful (test) stimulus applied to the contralateral extremity (a thermal stimulus at temperature previously calibrated to elicit pain with intensity of 60 on 0-100 NRS). Reduction of reported pain experience to test stimulus during conditioning is a surrogate measure of efficient descending pain modulation.

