At each of the intervention visits, an intravenous catheter will be inserted in the arm for drug administration, and in the opposite arm for obtaining blood samples to evaluate the plasma concentrations of lidocaine. The dose of lidocaine will be 5mg/kg ideal body weight (IBW), calculated by B. J. Devine Formula:

$$IBW = 50.0 + 2.3 \text{ kg per inch over 5 feet} \quad (\text{man})$$

$$IBW = 45.5 + 2.3 \text{ kg per inch over 5 feet} \quad (\text{woman})$$

Lidocaine will be infused during 40 minutes. The unblinded investigator will prepare 100mL normal saline infusion bags either with lidocaine or the same volume of normal saline (placebo). For lidocaine infusion, saline will be first drawn from the infusion bag in a volume equal to lidocaine volume to be added to the infusion, to keep the same total volume of the infusion bag. The total lidocaine dose will be limited to 500mg for safety reasons. The subjects will have continuous 3-lead ECG monitoring for 90 minutes.

Prior to infusion, we will assess:

1. Spontaneous pain intensity on 0-10 NRS.
2. NPSI pain descriptors burning, squeezing, pins and needles, tingling, stabbing, electrical shocks) on 0-10 scale
3. Evoked response (0-10 NRS) to cold (20°C, Rolltemp, Somedic), warm (40°C, Rolltemp, Somedic), brush (Senselab brush-05, Somedic) and pinprick (256mN metal probe, MRC Systems) stimuli applied to a dorsal foot and a non-painful control site (ipsilateral shoulder).

Tabular description of the study assessments is available in Table 1.

Table 1. Data assessment schedule

Required Assessments	Baseline visit	Treatment Visit 1	Washout			Treatment visit 2	Week 1b	Week 2b	Week 3b	End of Study communication
			Week 1a	Week 2a	Week 3a					
Informed consent	✓									
Inclusion/exclusion criteria	✓									
Randomization	✓									
Demographic data collection	✓									
BPI questionnaire	✓									
HADS questionnaire	✓									
Sensory Mapping	✓									
Assessment of sensitivity to cold, warm, brus and pinprick		✓				✓				
NoL measurement		✓				✓				
NPSI questionnaire		✓				✓				
QST		✓				✓				
CPM		✓				✓				
Blood sampling for PK		✓				✓				
Pain intensity 0-10 NRS		✓	daily	daily	daily	✓	daily	daily	daily	✓
Adverse Event assessment		✓				✓				✓
Blinding questionnaire										✓

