4.2 Sources of Materials

Subjects will be recruited from Washington University Diabetes Center and Pain Management Center.

Data on comorbidities and concomitant medication use are provided by subjects. Specimens include blood obtained exclusively for determining lidocaine plasma concentration. Other data including baseline quantitative sensory testing are obtained exclusively for research purposes.

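### The primary slope comparison leaves open the pairing of each patient's two responses, any period adjustment, and which visit's MPT or HPT is the predictor

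*Combined protocol and SAP*

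**What the plan says.** **Primary test.** Section 2.5.7 states: "We will perform t-test in a multiple linear regression model to test the difference between slopes of predictor magnitude vs. response magnitude". The synopsis and 2.5.7 then name the two slopes. The first is described as "Compare the slopes of MPT magnitude vs. lidocaine response magnitude (% reduction in pain intensity) curve"; the second is the same for placebo. HPT is handled in the same way. Neither place mentions a patient effect, a within-patient difference, a covariance structure, or a period or sequence term.

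**Design.** Section 2.5.1 has two intervention visits, "during which intravenous lidocaine or placebo infusion will be administered in a cross-over design", with the order randomised. Section 2.5.4 gives reduction of between-patient variability as the reason for the crossover. Section 2.5.8 continues enrolment until 35 participants have completed both phases.

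**Predictor.** The first aim in 2.3 is "To investigate whether the baseline mechanical pain threshold (MPT) predicts the individual response to intravenous lidocaine treatment in DPN"; the second is the same for HPT. Section 2.5.1 expects that, if the hypothesis is right, "then patients with higher MPT or HPT at baseline will have larger analgesic effect from lidocaine infusion". Section 4.2 also uses the word: "Other data including baseline quantitative sensory testing are obtained exclusively for research purposes". The procedures in 2.5.3, however, say of the two treatment visits: "At each of these visits the subjects will undergo a quantitative sensory testing procedure to determine the MPT and HPT parameters". In "Table 1. Data assessment schedule", QST is ticked at treatment visits 1 and 2 and not at the baseline visit. Section 2.5.6 averages three MPT readings within a session but gives no rule across visits.

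**The concern.** In a crossover, the comparison of lidocaine with placebo gains its precision from using each patient as their own control. If the two responses are entered as 70 separate observations, the standard error of the slope difference takes no account of their correlation. When that correlation is positive, the test is too cautious and a real predictor is more likely to be missed, so the stated reason for the crossover is not carried into its primary analysis. When it is negative, the test rejects too often.

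The second issue is the predictor. Each patient will have two MPT and two HPT values. Visit 1's value, the mean of the two, or each visit's own value set against that visit's response would all fit the text. With pairing and period adjustment also open, several primary p-values per predictor are compatible with the plan. The Bonferroni split in 2.5.8 covers the two predictors, not these choices.

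**Working it through.** **1. The plan's own figure.** Inputs from 2.5.8: difference 14, SD 18.21, power 85%, alpha 0.025 per predictor, 34 patients. Neither the sidedness nor the type of SD is stated. Noncentral-t calculations give:

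| Reading of SD 18.21 | One-sided 0.025 | Two-sided 0.025 |
|---|---|---|
| Within-patient SD, 2x2 crossover, variance 2 x SD²/n, n-2 df | 33 | 39 |
| Two independent sets, variance 2 x SD²/n, 2n-2 df | 32 per set | 38 per set |
| SD of the paired difference, variance SD²/n, n-1 df | 18 | 21 |

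The 34 is reproduced by the one-sided crossover reading (33, or 34 when made even for two sequences; power 0.867 at 34). The independent-sets reading comes almost as close, because it has the same variance and differs only in degrees of freedom. The figure therefore does not tell the two analyses apart.

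**2. Pooled against paired.** Let each patient have one predictor value x, residual SDs s_L and s_P under lidocaine and placebo, and residual correlation rho.

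- Both slopes are fitted on the same x values, so their difference equals the slope of (lidocaine minus placebo response) on x. The estimate is identical in the two fits.
- True and paired variance: (s_L² + s_P² - 2 rho s_L s_P)/Sxx.
- Variance that the pooled fit estimates: (s_L² + s_P²)/Sxx.
- Ratio of standard errors, pooled to paired: 1/sqrt(1 - 2 rho s_L s_P/(s_L² + s_P²)). With equal SDs this is 1/sqrt(1-rho).

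Equal SDs: 1/sqrt(0.7) = 1.20, 1/sqrt(0.5) = 1.41, 1/sqrt(0.3) = 1.83. At rho = -0.3: 1/sqrt(1.3) = 0.88.

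SD ratio 1.5: at rho 0.5, 1/sqrt(1 - 1.5/3.25) = 1.36 (1.37 in simulation); at rho 0.7, 1/sqrt(1 - 2.1/3.25) = 1.68.

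**3. Error rate and power.** Simulation with n = 35, two-sided 0.025 and unit residual variances. The pooled fit has 66 df and the paired fit 33. The slope difference of 0.6 residual SD per predictor SD is an assumption, as is the range of rho.

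| rho | Type I error, pooled | Type I error, paired | Power, pooled | Power, paired |
|---|---|---|---|---|
| 0 | 0.025 | 0.025 | 0.56 | 0.55 |
| 0.3 | 0.008 | 0.025 | 0.57 | 0.71 |
| 0.5 | 0.002 | 0.025 | 0.58 | 0.84 |
| 0.7 | 0.0002 | 0.025 | 0.60 | 0.97 |

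At rho = -0.3 the pooled type I error is 0.047 to 0.050 across separate runs, about twice nominal, while the paired test stays at about 0.025. If 0.025 is meant as one-sided, power at the same effect is 0.67, 0.70, 0.72, 0.77 pooled and 0.66, 0.80, 0.90, 0.98 paired. The pattern is the same.

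**4. Predictor value.** If each visit's own threshold is used, x differs between the two responses. The slope difference itself can then change, and the factor in step 2 no longer applies exactly. At an assumed single-visit reliability of 0.8 and effect 0.6, for rho 0, 0.3, 0.5 and 0.7:

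- pooled on own-visit values: power 0.45, 0.45, 0.45, 0.44;
- paired on the visit 1 value: 0.44, 0.59, 0.73, 0.90;
- paired on the mean of the two values: 0.49, 0.64, 0.79, 0.94.

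**The case against.** The strongest reply is that nothing in 2.5.7 prescribes a pooled fit. A multiple linear regression with patient indicators satisfies the wording and, with one predictor value per patient, is the paired test. A statistician analysing a declared crossover might well pair the data without being told. This stands: a reader might infer that the plan commits to an incorrect analysis, and the documents do not support that. It does not settle the predictor visit or the period term.

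The size of the loss is also open. The documents give no rho, no residual SDs and no standardised slope difference. The factor 1/sqrt(1-rho) assumes equal residual variances; for a given positive rho it is an upper bound, and unequal variances reduce it.

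A reader might take the 34 patients as evidence that a paired analysis was intended. Step 1 shows that it cannot bear that weight: 33 and 32 are too close to discriminate.

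A reader might also infer that the thresholds could be taken during or after an infusion. The text points the other way. The synopsis lists QST under baseline testing, apart from the repeated response testing, and 2.5.3 names only pain and evoked responses during the infusion. The list of pre-infusion assessments in 2.5.3 omits MPT and HPT, but what is really open is which visit's value counts.

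Finally, no benefit of period adjustment can be quantified, since the documents give no period effect. The case for it is that order is randomised and the adjustment is cheap.

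**Conclusion.** The primary analysis is under-specified on three points: pairing, period or sequence, and predictor visit. That can be read directly from the text and is secure. The consequence is conditional. If the literal pooled fit were used with one predictor value per patient and equal residual variances, the standard error would be 1.20, 1.41 or 1.83 times the paired one at rho 0.3, 0.5 or 0.7, and about 1.36 and 1.68 at rho 0.5 and 0.7 if the SDs differed by a factor of 1.5. At rho 0 nothing is lost. Below 0 the pooled test is anti-conservative. It would therefore be wrong to say either that the plan must lose power or that the pooled test is always safe; it holds its nominal level only at rho 0, whereas the paired test holds it throughout. All values of rho, effect size and reliability used here are assumptions. The point should be fixed before unblinding, because the remedy is cheap and concerns the primary test.

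**What to change.** In 2.5.7 and in the synopsis, replace the description of the primary test with wording such as: *For each predictor, the within-patient difference in response (lidocaine minus placebo) is regressed on the patient's pre-infusion threshold from treatment visit 1, with randomised sequence as covariate. The t-test of the predictor coefficient is the primary test.* State whether 0.025 is one- or two-sided.

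The visit 1 value precedes any study infusion and so fits the word baseline in the aims. The mean of the two visits' values can be a sensitivity analysis; it is more reliable but includes a threshold measured after the first infusion. A mixed model with treatment, that single predictor value, their interaction, period and a random patient effect is an acceptable equivalent. Its patient covariance should be allowed to be negative; otherwise it falls back to the pooled fit when the estimated rho is below zero.

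The cost is wording and one degree of freedom for sequence, about 0.01 to 0.02 of power if there is no period effect (for example 0.83 against 0.84 at rho 0.5 and effect 0.6). Using one visit instead of the mean of two costs about 0.04 to 0.06 of power at the assumed reliability of 0.8 (step 4). No new visits or measurements are needed. The difference requires a percentage reduction at both visits, so a patient with a pre-infusion score of zero or no usable outcome at a visit would need a stated rule; either analysis faces that gap.
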